5.4 Pharmacokinetic analysis set (PKS)

All finerenone-treated subjects (with the exception described in Section 5) with at least 1 valid finerenone plasma concentration and without validity findings which would interfere with the evaluation of the pharmacokinetic (PK) data.

5.5 Listing only set (LOS)

All other subjects enrolled who were not randomized or were excluded from FAS will be classified as LOS. Their data will be presented in the individual subject data listings but will not be included in any statistical analysis.

5.6 Assignment of analysis sets

The allocation of each subject to analysis sets will be documented before the database lock (conditional validity for PPS and PKS).

Final decisions regarding the assignment of subjects to analysis sets will be made during the validity review meetings and documented in the validity review reports.

If a subject has no signed informed consent or subject is a minor, then all data should be deleted from all databases and such a subject cannot be considered valid for any analysis set.

6. Statistical Methodology

6.1 Population characteristics

Population characteristic analyses, except for subject disposition, will be performed for the FAS, if not stated otherwise.

6.1.1 Disposition

The number of subjects enrolled, randomized and valid for the SAF, FAS, PPS and PKS will be summarized overall and by treatment group, region, country and study site. The number of subjects discontinuing each epoch, together with the primary reason for discontinuation will be presented by treatment group (post-randomization epochs only) and overall in separate tables. In addition, the number of subjects with important deviations and validity findings will

be presented overall and by country for each treatment group, and in total. The frequencies of each important deviation and validity finding will be presented by treatment group and in total.

6.1.2 Demography and other baseline characteristics

Demography includes age, age group (as defined in the subgroup analysis), sex, race, ethnicity, region (North America, Europe, Asia, Latin America and others; see section 9.3), body weight, body height, BMI, hip and waist circumference, waist-hip ratio, smoking history (never, former, current smoker) and alcohol consumption (abstinent, light, moderate, heavy). Other baseline characteristics include baseline UACR, serum potassium, categories for serum potassium (≤ 4.5 mmol/L and > 4.5 mmol/L), eGFR (calculated by CKD-EPI formula), serum creatinine, HbA1c, values for vital signs parameters (i.e. systolic blood pressure, diastolic blood pressure and heart rate) and additional subgroup categories as described in section 4.5.4.

All demographic data and baseline characteristics will be tabulated by treatment group and overall. The demographic and other baseline characteristics table will also be presented, separated by each level of the stratification factors.

The non-stratified demographic and other baseline characteristics table will be repeated for all other analysis sets.

As stated in section 4.2, demographics and other baseline characteristics will also be presented separately for subjects discontinuing the study (dropouts) and for subjects discontinuing treatment with study drug.

6.1.3 Medical History

Medical history will be coded using the MedDRA dictionary. Medical history will be presented for each MedDRA Primary System Organ Class and Preferred Term by treatment group and overall in a summary table. Additional medical history terms by the following Project specific Bayer MedDRA Queries (PBMQs), Bayer MedDRA Labeling Groupings (MLGs) or selected Preferred Terms will also be presented, including the following:

- Hyperlipidemia (MLG)
- Hypertension (MLG)
- Diabetic Retinopathy (Preferred Term)
- Diabetic Neuropathy (PBMQ)
- Atrial fibrillation/flutter (PBMQ)
- Ischaemic Stroke/Transitory Ischemic Attack (TIA) (PBMQ)
- Myocardial Infarction (Preferred Term)
- Coronary Artery Disease (Preferred Term)
- Myocardial Ischaemia and Angina pectoris (MLG)
- Peripheral Artery Disease (Preferred Term)
- Cardiac Failure (MLG)
- Coronary Artery Bypass Graft (CABG) (PBMQ)

- Percutaneous coronary intervention (PCI) (PBMQ)
- Carotid endarterectomy (Preferred Term)
- Periodontal disease (Preferred Term)

The medical history tables will be repeated for SAF.

6.1.4 Prior and Concomitant Medications

Concomitant medications will be coded using the WHO Drug Dictionary (WHO-DD). The number of subjects who took at least one concomitant medication, the number of subjects who took at least one medication that started and ended before administration of study drug, the number of subjects who took at least one concomitant medication that started after start of study drug and the number of subjects who took at least one medication ongoing at baseline (i.e. starting before or on the day randomization and ending at least one day after the day of randomization) will be presented by treatment group and overall using ATC classes and subclasses.

The concomitant medication tables will be repeated for SAF.

The concomitant medication tables will be repeated summarizing the number of subjects with medications in the Standard or Bayer Drug Groupings of interest:

- ACEIs
- ARBs
- Beta-blockers
- Diuretics
- Loop diuretics
- Thiazide diuretics
- Potassium-sparing diuretics
- Potassium supplements
- Potassium lowering agents (including binders)
- Alpha blocking agents
- Calcium channel blockers
- Centrally acting antihypertensives
- Strong CYP3A4 inhibitors
- Moderate CYP3A4 inhibitors
- Weak CYP3A4 inhibitors
- Unclassified CYP3A4 inhibitors
- Strong CYP3A4 inducers
- Moderate CYP3A4 inducers
- Weak CYP3A4 inducers
- Unclassified CYP3A4 inducers

- Oral anticoagulants
- NSAIDS (excluding acetylsalicylic acid)
- Acetylsalicylic acid and its salts
- Statins
- Erythropoetin stimulating agents
- ARNIs
- Platelet aggregation inhibitors (excluding heparin)

Anti-diabetic drugs

- Insulin and analogues
- Dipeptidyl Peptidase 4 inhibitors
- Glucagon-like peptide-1 agonists
- SGLT-2 inhibitors
- Biguanides
- Sulfonylureas
- Alpha glucosidase inhibitors
- Meglitinides
- Thiazolidinediones.

A subject will be counted only once within each ATC class / subclass or Bayer drug grouping, respectively.

A supporting listing will be provided including all medications classified as a weak, moderate or strong CYP3A4 inhibitors and inducers according to the protocol together with the respective classification information.

The percentage of patients who are on maximum labeled dose of ACEIs and ARBs (yes / no) 4 weeks before the Screening Visit, and reasons why not on maximum labeled dose will be presented by treatment group and overall. In addition, the percentage of patients at baseline above maximum, at maximum, between minimum and maximum, at minimum and below minimum labeled dose, using the dose ranges in Table 8-1 of the protocol, will be presented by treatment group and overall.

For potassium lowering agents, ACEIs, ARBs and diuretics, shift tables for changes of use for baseline vs. any time post-baseline will be provided.

6.1.5 Treatment duration, extent of exposure and compliance

The analyses described in this section will be repeated for the SAF and PPS if they differ in sample size from the FAS. All tables and figures regarding treatment duration, extent of exposure and compliance will be presented by treatment group and overall (unless otherwise stated).

Treatment duration, defined as time from start of study drug to permanent stop of study drug (in months) will be summarized using descriptive statistics by treatment group and overall. In addition, treatment duration will be categorized to ≤ 1 month, 1 - 4 months, then 4 monthly

intervals, and presented with the corresponding number and percentage of subjects. Cumulative treatment duration will be categorized to at least one dose, at least 1 month, at least 4 months, then further 4 monthly intervals. Cumulative treatment exposure over the study in person-years will be given. A table will be presented with the absolute and relative frequencies of subjects still on study medication at each visit. Kaplan-Meier plots for “Time to end of study treatment” will be provided by treatment group, as also described in section 4.2.

The above analyses will be repeated for study duration, from the day of randomization to the End of Study visit.

The extent of exposure to study drug (total amount of intake in grams) and the average daily dose in mg during treatment will be summarized using descriptive statistics by treatment group, also by eGFR category at screening.

The overall titration status, regardless of actual or sham up-titration, will be summarized with absolute and relative frequencies per treatment group, differentiated by patients starting on 10 mg or 20 mg:

- For subject starting on 10 mg: never up-titrated, up-titrated once, and up-titrated more than once.
- For subjects starting on 20 mg: never down-titrated, down-titrated once, and down-titrated more than once.

Furthermore, the dose status will be summarized with absolute and relative frequencies per treatment group for each visit with regard to the question “Was 20 mg study drug dispensed at visit?” and the reason why 20 mg was not dispensed. The number of subjects not dispensed with 20 mg as well as associated reason will also be presented overall, i.e. on the patient level.

In addition, the number of patients with study drug down-titrated to 10 mg or temporarily interrupted (dose recorded as 0 mg) as well as associated reason will be summarized with absolute and relative frequencies per treatment group.

The compliance (as percentage) will be calculated as follows:

$$100 * \text{Number of taken tablets} / \text{Number of planned tablets}$$

The number of planned tablets is calculated as follows:

$$(\text{Days from randomization to last intake of study drug} + 1) * \text{Number of planned tablets per day.}$$

All tablets, including the dummy placebo tablets, will be counted. For subjects who withdraw prematurely from the study drug, compliance will be calculated up to the time of last dose.

The compliance will be summarized descriptively by treatment group and overall. In addition, percent of compliance will be categorized into 3 groups, less than 80%, 80 to 120% and greater than 120%, and the categories will be summarized by treatment group and overall.

6.2 Efficacy

6.2.1 Analysis of primary efficacy variable

6.2.1.1 Primary efficacy variable: primary analysis

The primary efficacy variable is the time to first occurrence of the composite endpoint of onset of kidney failure, a sustained decrease of eGFR $\geq 40\%$ from baseline over at least 4 weeks, or renal death. All events classifying for the primary endpoint have to be adjudicated positively by an independent adjudication committee.

The primary analysis of the primary efficacy variable will be performed in the FAS.

Events for inclusion in the primary analysis will be counted from the day of randomization (planned at Visit 1) onwards until the EOS visit following the study termination decision, or until the date of EOS notification + 4 weeks, if the EOS visit has not been performed. In the event of premature discontinuation from the study with no subsequent follow-up information, renal events will be counted up to the day of the last visit when complete information on all components of the composite renal endpoint is available with an additional rule for events occurring after this visit. To account for events of kidney failure or renal death after the last eGFR is recorded at a clinic visit, such events will be included in the efficacy analysis if they occur in the period up to one day before the next planned clinic visit. This period would be a maximum of 5 months, given the next scheduled clinic visit should take place 4 months later, plus a time window for late attendance of one month. In addition, should the subject have a non-renal death in this period then the date of death will be used as the censoring date.

Randomized subjects without an event of the renal composite endpoint at the time of analysis will be censored at the date of their last visit when complete information on all components of the composite renal endpoint is available, up to and including the EOS visit (should this visit satisfy this rule), or date of non-renal death using a time window of 5 months as above if a subsequent clinic visit had been planned. Subjects without any information about the primary composite endpoint after baseline will be censored at Day 1.

The weighted Bonferroni-Holm procedure which will be used for the hierarchical testing of the primary and secondary efficacy endpoints, is described in section 4.7. In order to evaluate whether finerenone is superior to placebo in prolonging the time to the first event of the primary composite endpoint, the following null hypothesis will be tested using the logrank test at the two-sided significance level given above:

$$H_0: \lambda_{\text{finerenone},k}(t) = \lambda_{\text{placebo},k}(t) \text{ for all time points } t \geq 0 \text{ and each stratum } k$$

The alternative hypothesis will be:

$$H_1: \lambda_{\text{finerenone},k}(t) \neq \lambda_{\text{placebo},k}(t) \text{ for at least one time point } t \geq 0 \text{ and at least one stratum } k,$$

where $\lambda_{\text{finerenone},k}$ denotes the hazard rate of the finerenone treatment group in stratum k and $\lambda_{\text{placebo},k}$ denotes the hazard rate of the placebo treatment group in stratum k . In this context, the hazard rate is defined as the instantaneous risk of a primary composite event at a given time point provided that no such event has yet taken place. The test statistic of the stratified logrank test compares the observed number of events with the number of events expected under the null hypothesis H_0 in each treatment group per stratum.

The following decision rule to test the null hypothesis will be applied. According to the size of this study and the expected number of events, it is justified to assume under H_0 a sufficiently close approximation of the logrank test (see reference 4) to the normal

distribution. If the logrank test statistic (i.e. the standardized difference of the observed number of events and expected number of events stratified by the stratification factors region, type of albuminuria and eGFR category) is larger than the critical quantile from the normal distribution, the null hypothesis will be rejected in favor of the alternative hypothesis.

The nominal significance levels and the critical values at the final analysis will be adjusted to account for the interim analysis, see section 4.7 for more details.

In order to provide a point estimate of the hazard ratio and a corresponding two-sided 95% confidence interval, a stratified Cox proportional hazard regression model will be used. The stratification variables will be included in the STRATA statement in SAS PROC PHREG, which will assume proportional hazards for each level of one particular stratification factor.

Kaplan Meier curves will be provided for the cumulative incidence risk of outcome events by treatment groups.

To derive the logrank test statistic and the corresponding p-value, SAS program code corresponding to the following will be used:

```
PROC LIFETEST DATA = <dataset> ALPHA=0.05 METHOD=KM;
  TIME ttevalue * ttecnsr(1);
  STRATA {stratumn} / GROUP=trtgrpnr TEST=(logrank);
RUN;

/*
where
dataset = name of sub-dataset including all ITT subjects
randomized
trtgrpnr = variable coding randomized treatment group
ttevalue = time to first occurrence of primary efficacy
outcome event
ttecnsr = censoring index (1 = right-censored, 0 = event)
stratumn = variables for stratification factors
*/
```

For the Cox proportional hazard regression SAS program code corresponding to the following will be used:

```
PROC PHREG DATA = <dataset>;
  MODEL ttevalue * ttecnsr(1) = trtgrpnr / RL TIES=EFRON
ALPHA=0.05;
  STRATA {stratumn};
RUN;
```

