The presence of albuminuria in an individual is highly predictive of CV events and progression of kidney disease. In ARTS-DN (study 16243) in patients with T2DM and DKD treated with finerenone in combination with SoC therapy using a RAS inhibitor, a dose-dependent reduction in UACR from baseline to Day 90 was demonstrated. Statistically significant reductions in UACR of 21%, 25%, 33% and 38% at Day 90 compared to baseline were observed for the 4 highest doses of finerenone (7.5, 10 mg, 15 mg, and 20 mg od, respectively) compared to placebo. In a post hoc analysis, UACR decreases of ≥ 30% from baseline to Day 90 in the placebo, 7.5 mg, 10 mg, 15 mg and 20 mg groups were seen for 23.9%, 40.2%, 46.0%, 51.3% and 62.5% of subjects, respectively, and UACR decreases of ≥ 50% in the same groups were seen for 13.6%, 17.2%, 17.2%, 33.6% and 40.2% of subjects, respectively. Post-hoc analyses of randomized clinical trials (33, 34) suggest that a meaningful reduction in albuminuria may translate to protection from CV events and declining renal function in patients with diabetic and non-diabetic renal disease with albuminuria. For every 30% reduction in albuminuria, the risk of ESRD decreased by 23.7% (95% confidence interval, 11.4% to 34.2%; p=0.001) (33); there was an 18% reduction in CV risk and 27% reduction in HF risk for every 50% reduction in albuminuria (34).

Due to finerenone's mode of action, hyperkalemia is an important identified risk which was also identified from previous studies with finerenone. Patients with pre-existing impairment of their renal function are likely to have a greater risk of experiencing clinically significant hyperkalemia. A greater risk for hyperkalemia may also occur if drugs which raise the potassium concentration (e.g. ACEI, ARBs or potassium-sparing diuretics) are used concomitantly.

Worsening of renal function has been shown to occur with the steroidal MRAs, i.e. spironolactone and eplerenone, as well as RAS blocker in general.

The risk for such adverse events with finerenone is not ruled out. However, in ARTS-DN, the incidence of hyperkalemia was low, and the incidence of eGFR decline ≥ 30% relative to

baseline was similar between placebo and finerenone groups, with no imbalance in reported AEs related to the MedDRA primary system organ class '*Renal and urinary disorders*'. In ARTS (study 14563), all doses of finerenone resulted in significantly lower potassium increase and less eGFR reduction compared to spironolactone.

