- Delays the time to first occurrence of the following composite endpoint: onset of kidney failure, a sustained decrease of eGFR $\geq 57\%$ from baseline over at least 4 weeks, or renal death.

5. Study design - amended

This section was changed in Amendment 3, see Section 15.1.2.3.

Design overview

Study 16244 is a randomized, double-blind, placebo-controlled, parallel-group, multicenter, event-driven Phase III study. [Figure 5–1](#) displays the overall study design.

Patients from approximately 900 study centers worldwide will be randomized in a 1:1 ratio to either finerenone or placebo in addition to SoC therapy. Assuming a screening failure rate of approximately 50%, 9600 patients will have to be screened to randomize approximately 4800 patients.

The anticipated duration of the study is approximately 4 years: this includes an anticipated recruitment period of 2.75 years followed by a study drug treatment period of 1 year after the enrolment of the last patient into the trial and a maximum of 4.5 months for the run-in and screening period and 1 month for the follow-up period. However, as an event-driven trial, the actual length of the trial will depend on the observed event rates, the patient recruitment rate, and length of the recruitment period.

Since all randomized subjects belong to the Full Analysis Set (FAS) on which the efficacy analyses are based, it is important to avoid randomization of non-eligible subjects into the study.

Run-in Period (4 up to 16 weeks)

Subjects with written informed consent who complete the Run-in Visit and meet all eligibility³ criteria will be enrolled into a mandatory Run-in Period, the purpose of which is to ensure that the subject's SoC therapy including treatment with ACEIs or ARBs is optimized and that all inclusion and exclusion criteria are met at the Screening Visit. The Run-in Period will last for a minimum of 4 weeks and a maximum of 16 weeks.

In the absence of documentation of diagnosis of high or very high albuminuria (see [Section 3.1](#) for definition), the subject may still be enrolled into the study as albuminuria will be measured at the Run-in Visit; in this case, the Run-in Period must last for a minimum of 12 weeks and a maximum of 16 weeks.

Screening Period (up to 2 weeks)

[figure not shown]

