7.3 Treatment assignment

Eligible subjects will be randomized within ≤ 2 weeks after the Screening Visit. The randomization will be stratified by region (North America, Europe, Asia, Latin America and others), type of albuminuria at screening (high or very high albuminuria) and eGFR at screening (25 to <45 , 45 to <60 , ≥ 60 mL/min/1.73m²). The eGFR will be calculated by the Central Laboratory applying the CKD-EPI formula (36).

The number of subjects with eGFR ≥ 60 to <75 mL/min/1.73 m² and very high albuminuria will be capped at approximately 10% of the total population with very high albuminuria at screening. The number of subjects with high albuminuria and presence of diabetic retinopathy in the medical history will be capped at approximately 10% of the total population at screening.

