10.4 Determination of sample size - amended

This section was changed in Amendment 3, see Section 15.1.2.41.

This is an event-driven study. A total of 1068 primary efficacy endpoint events will have a minimum 90% power to demonstrate superiority of finerenone to placebo using a logrank test at a two-sided significance level of 3.3333%, assuming a 20% relative risk reduction, i.e. a true hazard ratio of 0.80 (the hazard ratio that will be observed in the study will be different, i.e. closer to 1 due to treatment discontinuations). The study will stop when at least 1068 primary efficacy endpoints accrue across both treatment arms.

With an assumed treatment duration of 44 months (duration of recruitment period: 33 months, equal recruitment pattern during the accrual period, maximum treatment period of the last subject recruited: 11 months), the planned total number of subjects to be randomized is estimated to be 4690 subjects, assuming an annual placebo event rate of 12%, a common annual lost-to-follow-up rate of 0.7% in both treatment groups, an annual finerenone discontinuation rate of 5% and assuming that placebo discontinuation will not change the hazard. 4800 subjects are planned to be randomized taking a certain ramp-up during recruitment into account. Assuming a screening failure rate of 50%, 9600 subjects are planned to be screened.

Due to the minimal effect of the interim analysis on the overall power of the study, an adjustment of sample size would be negligible.

The assumption of the annual placebo event rate of 12% is based on a recent analysis of the results from the IDNT and RENAAL trials using alternative endpoints defined by smaller declines in eGFR, similar to those proposed in Study 16244. Event rates were obtained from the respective studies in the arms where treatment would more closely resemble that in the placebo population of study 16244 who will be on standard of care treatment for DKD. Annual event rates for the composite renal endpoint range from 11-16% for these studies. The planned population of study 16244 will have some differences compared to IDNT and RENAAL, with a likely lower median UACR value but comparable mean eGFR. The comorbidity of diabetic retinopathy in subjects with high albuminuria may predict a higher

rate of renal events. Consequently, the assumed annual placebo event rate of 12% is assumed to be appropriate for this Phase III setting (10, 11).

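### The primary test and hazard ratio use albuminuria only as a two-level stratum; adjusting for measured baseline UACR would recover a modest amount of power

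*SAP*

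**What the plan says.** SAP 6.2.1.1 tests the primary endpoint with a log-rank statistic "stratified by the stratification factors region, type of albuminuria and eGFR category". For the hazard ratio it states that "The stratification variables will be included in the STRATA statement in SAS PROC PHREG", and the code beneath has treatment as the only term in the MODEL statement. The stratification factors are those of the randomization.

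Type of albuminuria has two levels, high and very high. Protocol 7.3 says "The number of subjects with high albuminuria and presence of diabetic retinopathy in the medical history will be capped at approximately 10" percent, with all subjects as the denominator. Protocol 6.1 starts the very high level at 300 mg/g, and Protocol 6.2 excludes UACR above 5000 mg/g.

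The supportive analyses of the primary endpoint in SAP 6.2.1.2 are the per-protocol, on-treatment and unstratified analyses, the proportional hazards check and the tipping point. None adds UACR. In SAP 4.5.4 baseline UACR appears among the subgroups, split at its median and also classed as albuminuria type at baseline. By contrast, log baseline UACR is a covariate, nested in albuminuria type, in the Month 4 ANCOVA (SAP 6.2.2.1) and in the UACR mixed model (SAP 6.2.3.2).

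**The concern.** The documents themselves treat the level of albuminuria as informative about the outcome. Protocol 3.2 calls it an independent risk factor for progression, and Protocol 3.3 calls it highly predictive. Protocol 10.4 weighs the expected median UACR when it sets the placebo event rate. SAP Figure 1-1 divides the very high range again at 2000 mg/g. Yet within each region and eGFR cell, the primary analysis treats a subject at 300 mg/g and one at 5000 mg/g as exchangeable.

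In a proportional hazards setting, leaving out a prognostic covariate pulls the estimated hazard ratio towards 1 and costs power, even under perfect randomization. The value is already collected. SAP 4.5.3 takes it on or before the day of randomization, with the screening samples as fallback, so it is a valid baseline covariate. At stake is a small amount of power in an event-driven trial whose event rate was slower than assumed (SAP section 3).

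**Working it through.** **Inputs from the documents.** Protocol 10.4: "A total of 1068 primary efficacy endpoint events will have a minimum 90% power", "using a logrank test at a two-sided significance level of 3.3333"%, "a true hazard ratio of 0.80" diluted by 5% per year finerenone discontinuation, 12% annual placebo event rate, 0.7% annual loss to follow-up, 33 months of uniform accrual plus 11 months, N = 4690. Protocol section 5: subjects are "randomized in a 1:1 ratio to either finerenone or placebo".

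**Step 1: reproduce the plan's figure.** With z(0.98333) = 2.128 and z(0.90) = 1.282, the undiluted event counts are:
- Schoenfeld: 4 × (2.128 + 1.282)² / (ln 0.80)² = 934
- Freedman: (2.128 + 1.282)² × (1.80/0.20)² = 942

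A Lakatos-type calculation with the stated discontinuation and loss gives 1067 to 1071 events, N of 4688 to 4702 and an average hazard ratio of about 0.811. At 1068 events and a hazard ratio of 0.8115, power is 90.1%. The plan's 1068 and 4690 therefore reproduce, with almost no slack above 90%.

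**Step 2: width of the very high level.** 5000/300 = 16.7-fold, and ln(16.7)/ln 2 is about 4.06 doublings.

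**Step 3: cost of leaving UACR out.** The documents give no hazard ratio per unit of baseline UACR, so the following are assumptions:
- the hazard rises by a factor of 1.25, 1.5 or 1.75 per doubling of UACR (hazard proportional to UACR^b, with b = ln(factor)/ln 2, about 0.32 to 0.81);
- 90% of subjects are in the very high level, with ln UACR truncated normal between 300 and 5000 mg/g, median parameter 950 mg/g and SD about 0.65;
- region and eGFR cell shares are assumed and have no effect on the hazard.

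For each case 3000 trials were simulated and stopped at 1068 events. The planned stratified log-rank test was compared, on the same trials, with the stratified Cox model plus log UACR, at two-sided 3.3333%.

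| HR per doubling | Power, planned | Power, adjusted | HR, planned / adjusted | Relative efficiency | Equivalent events |
|---|---|---|---|---|---|
| 1.0 (check) | 89.5% | 89.6% | 0.8122 / 0.8122 | 0.996 | 1072 |
| 1.25 | 89.1% | 89.3% | 0.8132 / 0.8121 | 1.008 | 1059 |
| 1.5 | 88.4% | 89.7% | 0.8162 / 0.8124 | 1.041 | 1026 |
| 1.75 | 87.5% | 90.3% | 0.8194 / 0.8119 | 1.087 | 982 |

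Monte Carlo error on each power is about 0.5 point. Equivalent events are 1068 divided by the relative efficiency. The saving runs from (1068 − 1059)/1068 = 0.8% to (1068 − 982)/1068 = 8.1%. With ln UACR uniform over 300 to 5000 mg/g, the 1.5 case gives 88.9% against 90.9%.

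**Step 4: mechanism.** The standard error of the log hazard ratio is about 0.062 in both models, so the loss comes from attenuation. At 1.75 per doubling, (ln 0.8119 / ln 0.8194)² = (0.2084/0.1992)², about 1.09, in line with the simulated 1.087.

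**Step 5: the other reading of 0.80.** Suppose the design effect is what the planned test itself estimates, so that the planned test has exactly 90%. Adjusted power is then Φ(3.410 × √RE − 2.128), where RE is the relative efficiency. This gives 90.2%, 91.2% and 92.3% at 1.25, 1.5 and 1.75.

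**The case against.** The strongest reply is that nothing here is wrong. Stratifying by the randomization factors is coherent, assumes no functional form for UACR, and matches the test for which the events were calculated. Protocol 10.4 states the 0.80 for a log-rank test, and 1068 events deliver about 90% without any covariate. On that reading, adjustment is a bonus. This stands: a reader might infer that the trial is underpowered or that 1068 is miscalculated, and the documents do not support either.

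The size also rests on an assumed gradient. It is tempting to take one from Protocol 3.3, "For every 30% reduction in albuminuria, the risk of ESRD decreased by 23.7"%, which would give ln(0.763)/ln(0.70) = 0.758, or about 1.69 per doubling. That statement concerns reduction in albuminuria, comes from post hoc analyses, and is about ESRD alone. It is not a gradient across subjects in baseline UACR for a composite that also counts a sustained 40% fall in eGFR. Losses of 5 to 6 points do appear in the simulation at 2.0 per doubling (85.1% against 90.0%, or 84.3% against 90.1% with uniform ln UACR), but no document supports a gradient that steep.

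Three further limits are fair:
- Baseline UACR is not ignored throughout the SAP, since it is a key subgroup factor with an interaction test.
- The SAP does not use it in every UACR model: the logistic regressions for the categorical UACR variables (SAP 6.2.3.2 and 6.2.3.5) list only treatment and stratification levels.
- The 90% share one level of one factor, not one stratum, because region and eGFR category divide them further.

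None of this removes the gain from using a prognostic baseline value that is already in hand.

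**Conclusion.** The point holds as a missed efficiency. The primary test and hazard ratio use albuminuria only in two levels, about 90% or more of subjects are in one of them, and no planned primary or supportive time-to-event model adjusts for measured UACR. Under 1.25 to 1.75 per doubling, adjustment is worth about 0.2 to 3 points of power, or about 1% to 8% of events, and moves the hazard ratio by about 0.01 or less. At the weak end the gain is negligible.

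The figures rest on the assumed gradient and UACR distribution and on N = 4690. The SAP later raised N to about 5800 with the event target unchanged. The simulation fitted a single log UACR slope across both albuminuria levels; the nested form recommended below was not run separately.

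**What to change.** Before unblinding, add log baseline UACR, nested in albuminuria type as in the Month 4 ANCOVA of SAP 6.2.2.1, to the MODEL statement of the stratified PHREG. Do this for the primary endpoint and for the 57% renal composite. The existing STRATA statement stays, and the screening fallback for baseline UACR in SAP 4.5.3 already applies.

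- **Preferred:** take the confirmatory test from this model and keep the stratified log-rank test as supportive. Protocol 10.3.3.1 names the log-rank test, so this needs a protocol amendment as well as SAP text. The same test should be used at the interim and final analyses. The tipping-point analysis in SAP 6.2.1.2 reuses the primary Cox model and would follow.
- **Minimum:** pre-specify the adjusted model as a named supportive analysis. This costs SAP wording and a covariate in the code, and leaves alpha, the event target and the primary test unchanged. It recovers no confirmatory power, but it gives a planned adjusted estimate that would otherwise be post hoc.

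The downsides are that the hazard ratio becomes conditional on UACR and that a log-linear form is assumed. Continuous baseline eGFR is not part of this recommendation, because its effect was not evaluated.
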